Title

The Effectiveness of Telehealth program on Cardiac Symptom Distress, Self-care and Quality of Life in Patients with Coronary Artery Disease after Coronary Artery Bypass Surgery: A Randomized Controlled Trial

NCT Number: NCT06648291

Version Number: Version 3

Document Date: 2023/08/09

1. Introduction

Cardiovascular disease accounts for over 30% of global deaths, 40% of which are caused by coronary artery disease (CAD) (CDC , 2024; Pooria et al., 2020) and that the number of deaths caused by CAD surged to 3.7 million in 2021 (American Heart Association [AHA], 2024). Coronary artery bypass grafting (CABG) is one of the most widely performed surgical procedures for treating CAD, with approximately 8 million CABG surgeries conducted globally each year (Gohari et al., 2022). Although the success rate of CABG has improved, patients still encounter numerous physical, psychological, and social challenges after discharge. Physical issues include, but not limited to, pain at the chest or leg incision site, difficulty breathing, sleep disturbances, fatigue, weakness, and loss of appetite. Psychological challenges encompass depression, anxiety, and stress caused by changes in social and occupational life (Ilgin et al., 2024). These symptoms may persist for weeks and, if unresolved, could mask worsening wound pain, infection, or weakness from malnutrition (Khodaveisi et al., 2020). According to a study by Montrief et al. (2018), 7% of CABG patients experience multiple emergency visits and readmissions within one month post-surgery, due to chest pain, wound infections, and heart failure. Given these challenges, patients undergoing heart surgery should be educated and learn self-care skills to manage the problems they may face in the future (Veronovici et al., 2014).

The ability to self-care is critical to promote recovery and reduce symptom severity in

CABG patients (Alkuwaisi et al., 2024). For patients following cardiovascular surgery, the implementation of self-care activities includes healthy eating habits, regular exercise, smoking cessation, weight control, and adherence to prescribed medications (Tippinit & Polsook, 2023; Knuuti et al., 2020). Prior studies have shown a positive association between self-care behaviors and knowledge, suggesting that those patients who gain sufficient knowledge about disease management are more likely to perform effective self-care behaviors (Kassahun et al., 2016). However, the length of hospital stay for patients following CABG is decreasing, with the average discharge time being day 7 post-surgery, the time to prepare for discharge is limited, and patients are discharged with a large amount of information from healthcare professionals, which is not fully absorbed by the patient and is stressful (Lin et al., 2024; Steenbergen et al., 2022). As a result, patients often have poorer self-care behaviors during the transition from hospital to home, which in turn affects quality of life after discharge (Hundiyawati et al., 2023).

Quality of life is the ability of individuals to function normally and feel satisfied with their capacity to engage in daily activities. This includes being physically active, maintaining independence, assisting others, participating in social interactions, achieving emotional stability, being free from pain or other symptoms of discomfort, and having adequate sleep and rest (Pačarić et al., 2020). Studies have shown that approximately 25% of CABG patients experience a decline in quality of life after surgery due to deterioration in overall health status

and the body's reduced ability to function as they did before surgery. This decline often results in poor disease compliance and unhealthy lifestyle habits (Nobari et al., 2021; Kidd et al., 2016). Nair et al. (2018), in a study tracking the lifestyle and health problems of 500 CABG patients six months after surgery, found that only 11.6% maintained a healthy lifestyle. The associated risk factors include obesity, poor glycemic control, hypertension, and high cholesterol, affecting 9.6%, 20.2%, 35%, and 48.4% of patients, respectively. Postoperative recovery and quality of life largely depend on how well patients manage these risk factors (Mohesnipouya et al., 2016). Therefore, it is crucial to provide ongoing counseling and health education to help patients acquire the necessary self-care knowledge and skills, and encourage them to adopt a healthier lifestyle (Nobari et al., 2021).

With the rapid development of smartphones and related device technologies, remote monitoring for patients with various diseases has become increasingly common. This is particularly evident in the home-based follow-up care of patients discharged after cardiac surgery, which has emerged as a growing trend (Sarkar et al., 2022). Telehealth programs encompass a wide range of health-related services that utilize electronic and communication technologies to remotely deliver health or medical information (Dosaj et al., 2021). In this model, nurses play a crucial role by providing supportive care, continuous monitoring, evidence-based professional guidance, health education, effective counseling, and follow-up services (Zhou et al., 2023; Gimenez et al., 2024). Moriyama et al. (2021) emphasized that

telenursing can improve the lifestyles of patients with chronic diseases and help manage cardiovascular conditions. Several studies have shown that telehealth can reduce healthcare costs, decrease emergency room visits, readmission rates, and mortality (Purcell et al., 2014; Scalvini et al., 2018; Dawson et al., 2021), Telehealth has also been shown to be more effective than conventional care in motivating patients to engage in self-care (Kotsani et al., 2018), and to improve patient compliance and self-efficacy (Gohari et al., 2022; Bikmoradi et al., 2016; Bikmoradi et al., 2017). However, research on the impact of telehealth program cardiac symptom distress, self-care behaviors, and quality of life in post-CABG patients remains limited. The purpose of this study was to examine the effect of telehealth services on symptom distress, self-care behaviors, and quality of life in patients discharged after undergoing CABG. We hypothesized that telehealth program will alleviate symptomatic distress, enhance self-care, and improve quality of life.

2. Methods

2.1 Study Design

A randomized controlled trial (RCT) was conducted in a teaching hospital in northern Taiwan using a two-parallel-group design. Participants were recruited postoperatively and randomly assigned to either the experimental or control group before hospital discharge. Following discharge, the experimental group received a 4-week telehealth care intervention, whereas the control group received standard care only.

2.2 Participants recruitment

Participants were recruited between September 2023 and January 2025 from the cardiac surgery ward at the National Taiwan University Hospital. The inclusion criteria for the study were: 1) 18 years of age or older; 2) underwent CABG for the first-time; 3) ability to read and respond to questionnaires; and 4) possession of an internet-enabled mobile device (e.g., smartphone or tablet). The exclusion criteria were: 1) cognitive impairment that prevents clear communication; and 2) being bedridden or physically disabled, unable to care for oneself.

2.3 Randomization

Eligible patients were provided with detailed information about the study and its objectives. Those who agree to participate were randomly assigned to the experimental group or the control group in a 1:1 ratio. The random numbers were generated by an independent person using a random number generator. Sealed envelopes were used to ensure allocation concealment. Due to the need for the experimental group to download and learn the electrocardiogram equipment, participant blinding was not feasible. However, the primary care physician and nurses are blinded to the allocation of the two groups.

2.4 Ethical consideration and study registration

This study was approved by the Ethics Committee of the National Taiwan University Hospital (approval number: 202307014RINA, approval date: August 4, 2023). Written informed consent was obtained from all participants. All data were anonymized to maintain confidentiality and were securely stored in locked file cabinets. Participants were informed

that they had the right to withdraw from the study at any time without the need to provide any reason.

2.5 Sample size

The sample size was calculated using the effect size 0.50 from a similar study by Nobari et al. (2021), with G Power-3.1.9.2, the significance level at 0.05, and the power at 0.80, resulting in a minimum required sample size of 128 subjects. Considering potential attrition, an additional 20% subjects was included. Therefore, the total sample size was 160 patients, with 80 patients in the experimental group and 80 patients in the control group.

2.6 The control group

Patients in the control group received standard care and were instructed by the ward nurses on nursing care, including wound assessment, education on diet, exercise, bathing, and medication, according to the post-coronary artery bypass surgery hygiene manual developed by the hospital. They were also instructed to monitor their blood pressure, blood glucose levels, and weight daily, and were scheduled for a follow-up phone call on the seventh day after discharge

2.7 The intervention group

In addition to standard care, starting from the day of discharge from the hospital, patients in the intervention group were scheduled for telephone interviews every three days, conducted by nine well-trained telenursing specialists. Each interview lasted approximately 10 to 15 minutes, for four weeks. The objective of these telephone interviews was to encourage and monitor the patients' adherence to effective self-health management practices, which included: (1) assessing daily blood pressure, weight, blood glucose levels, and lower

limb edema; (2) providing counseling on medication adherence, physical activity, and dietary hygiene; (3) offering guidance on wound care; (4) advising on the avoidance of cardiovascular risk factors, including smoking and exposure to secondhand smoke, as well as facilitating referrals to appropriate outpatient services, such as nutrition or rehabilitation clinics, based on individual needs. Additionally, patients were provided with a portable electrocardiogram device (ecg103, Quanta Computer Inc, Taipei, Taiwan).

During hospitalization, the research team assisted in installing the ECG software on the patient's mobile device and provided demonstrations until the patient was proficient in independently operating the device. A detailed operation manual was provided, which instructed the patient to measure ECG once in the morning and once in the evening. Patients were instructed to upload ECG data immediately if experiencing chest discomfort. The patient was provided with the website and operating procedures of the telehealth platform. The patient was also instructed to input daily physiological data, including blood pressure and blood glucose levels. Should any abnormalities in heart rhythms, blood pressure, or glucose levels be detected, the researcher contacted with the patient to assess their clinical condition and provide 24-hour online counseling.

2.8 Data collection

Outcomes were evaluated at three time points: two days before discharge (baseline, T0), at the first outpatient visit (7–10 days post-discharge, T1), and at the end of the intervention (4 weeks post-discharge, T2).

2.8.1 Demographic

Demographic questionnaires included gender, age, education, marital status, occupation,

and economic status, place of residence, smoking history, and alcohol consumption, combined valve surgery, and presence of comorbidities.

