2.9 Data analysis

Descriptive statistics of continuous variables are presented in mean and standard deviation (SD). Categorical variables are presented using frequencies and percentages. A Pearson's chi-square test or Fisher's exact test was used to analyze categorical variables, depending on whether the expected cell count was less than five. Continuous variables were compared using the independent t test. The paired t test was applied to compare the means

of the scores in each group before and after the interventions, and the independent t-test to compare the means of the scores in the two groups. To analyze the changes in cardiac symptom distress, self-care, and quality of life at different time points for the same study participant, the analysis was performed using the generalized estimating equations (GEE). An overall alpha-level of 0.05 was used as for statistical significance and all statistical tests were two-tailed. Statistical analyses were performed in SPSS versi

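### The stated between-group comparison is an unadjusted t-test although the T0 score, age, valve surgery and comorbidity are all recorded; a specified adjusted model would be more precise

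*Combined protocol and SAP*

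**What the plan says.** - **Population.** Section 2.2 requires a first CABG and does not exclude a valve procedure at the same operation. Section 2.8.1 expects such patients: besides age, it records "combined valve surgery, and presence of comorbidities".
- **Allocation.** Section 2.3 gives 1:1 allocation and says: "The random numbers were generated by an independent person using a random number generator". It names no stratification factor.
- **Timing.** Section 2.8 measures the outcomes two days before discharge (T0), 7–10 days after discharge (T1) and 4 weeks after discharge (T2). A baseline score therefore exists for every outcome.
- **Analysis.** Section 2.9 uses "the independent t-test to compare the means of the scores in the two groups". It also uses GEE for change across time points, but states no model terms, covariates or working correlation.
- **Sample size.** Section 2.5 says: "The sample size was calculated using the effect size 0.50 from a similar study", with "the significance level at 0.05, and the power at 0.80". It mentions no covariate adjustment.

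**The concern.** An independent t-test cannot take covariates. Whatever the T0 score, age, extent of surgery and comorbidity explain of the later scores stays in the residual and widens the interval. A larger operation, older age and comorbidity could plausibly slow recovery at home. T0 is taken in hospital and may capture only part of that.

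The GEE could use this information, but section 2.9 does not say whether it does. Nor does it say whether T0 is a response or a covariate, and the working shows that this decides whether adjustment helps at all. With the terms left open, covariates could also be picked after the baseline comparisons have been seen.

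**Working it through.** **1. The plan's own figure.** Inputs from 2.5 and 2.9: difference 0.50 SD, alpha 0.05, power 0.80, and "all statistical tests were two-tailed". The two-sample t calculation gives 63.77 per arm, so 64 per arm and 128 in total, as stated. Allowing for 20% attrition, 128 / (1 − 0.20) = 160, as stated. Power at 64 per arm is 0.801. The sample size is not in question.

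**2. Power after adjustment.** The documents give no R², the share of outcome variance explained by the covariates, so it is assumed. With k covariates and 128 patients, df = 126 − k. The noncentrality is [0.50 / √(1 − R²)] × √(64/2) × √[(df − 1)/(df − 1 + k)], where the last factor is the approximate cost of fitting.

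| Adjustment | Assumed R² | Noncentrality | Power |
|---|---|---|---|
| None | 0 | 2.828 | 0.801 |
| T0 score, correlation 0.3 (k = 1) | 0.09 | 2.953 | 0.834 |
| T0 score, correlation 0.5 (k = 1) | 0.25 | 3.253 | 0.898 |
| Valve, age, comorbidity (k = 3) | 0 | 2.794 | 0.792 |
| Same | 0.05 | 2.867 | 0.812 |
| Same | 0.10 | 2.945 | 0.832 |
| Same | 0.15 | 3.031 | 0.853 |

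Ignoring the fitting cost, the two T0 rows are 0.837 and 0.900.

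**3. What the factors add once T0 is in the model.** This was simulated with 150 runs per setting, 64 per arm, three visits, complete data, exchangeable correlation and a true T2 effect of 0.50. One covariate explains the same R² at every visit. Mean standard errors of the T2 comparison:

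| R², within-patient correlation | Unadjusted | Covariate | T0 | Both |
|---|---|---|---|---|
| 0.10, 0.5 | 0.176 | 0.168 | 0.153 | 0.151 |
| 0.20, 0.5 | 0.177 | 0.159 | 0.154 | 0.148 |
| 0.20, 0.3 | 0.176 | 0.158 | 0.169 | 0.158 |

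At correlation 0.5, T0 gives most of the gain. In the second row the covariate then cuts variance by a further 1 − (0.148/0.154)² = about 8%. At correlation 0.3 with R² = 0.20 the order reverses and the covariate does more than T0.

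**4. Why the GEE terms matter.** In the same simulation, a GEE with T0, T1 and T2 all as responses and the effect read from arm-by-visit gave a T2 standard error of 0.175 at R² = 0.20 and correlation 0.5, with or without the covariate as a main effect. The estimate did not change either. At correlation 0.3 the standard error was 0.207 both ways, worse than the unadjusted T2 comparison (0.176). Adding fixed covariates to that model gains nothing with complete data.

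**5. Chance imbalance in valve surgery.** With unrestricted allocation (assumed) and 80 per arm, the probability of an imbalance of 10 percentage points or more is 4.8%, 13.8% and 19.5% for assumed prevalences of 10%, 20% and 30%. If valve surgery moves the score by 0.2 to 0.5 SD, such an imbalance shifts the estimate by 0.10 × 0.2 = 0.02 to 0.10 × 0.5 = 0.05 SD. The standard error at 64 per arm is √(2/64) = 0.177 SD.

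**The case against.** - **The GEE may already be adjusted.** A reader might infer that the recorded factors are left out of every treatment comparison. The documents do not show that. The GEE terms are unstated, so covariates are neither included nor excluded, and the available text of 2.9 breaks off at the software version. What stands is that no comparison names a covariate and that the stated t-test cannot carry one.
- **Randomisation already protects the comparison.** A reader might also infer that mixing valve and CABG-only patients without stratification biases the result. It does not: the unadjusted comparison is valid on average, and chance imbalance is covered by its error rate and interval. Large shifts need high prevalence, a strong effect and an unlucky allocation together. Imbalance is a minor argument here.
- **The gain may be small.** This stands in part. The documents give neither R² nor the T0 correlation. The correlation could be low for SF-12, whose four-week recall at T0 reaches back before much of the recovery. The prognostic argument is also weaker for self-care and mental quality of life than for symptoms and physical quality of life. Against this, the simulated covariate acted equally at every visit, T0 included. A factor that affects recovery at home but not T0 would add more than step 3 shows.
- **Prespecification may be late.** Section 2.2 reports recruitment to January 2025 in the past tense. The set can still be fixed before outcomes are compared, if that has not yet happened.

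**Conclusion.** The point holds as a weakness of efficiency and specification, not of validity. The stated between-group test ignores baseline information the trial already collects, and the GEE that could use it is not specified.

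At 64 per arm and 0.50 SD, T0 adjustment alone is worth about 3 to 10 power points for correlations of 0.3 to 0.5. The three other factors alone are worth about 1 to 5 points for R² of 0.05 to 0.15, and at correlation 0.5 they add less after T0. The downside is about one point if those three are not prognostic. R², the T0 correlation, valve-surgery prevalence and its effect are all assumptions. None of this makes the planned 128 or 160 wrong.

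**What to change.** In 2.9, for each outcome score:

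- Take the treatment effect at T1 and at T2 from a GEE with only T1 and T2 as responses. State that T0 is not also a response.
- Include arm, visit, arm-by-visit, the T0 score of the same outcome, combined valve surgery (yes/no), age (continuous) and comorbidity in one stated coding, such as a count. Section 2.8.1 says only that presence is recorded, so the coding must be written down.
- State the working correlation.
- Fix the set before any outcome comparison and do not choose it from baseline p-values. If comparisons have already been run, label the adjusted analysis as post hoc.
- Report the unadjusted t-test as supportive.

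The cost is a short paragraph in 2.9 and a coding rule for comorbidity. It needs no new data, patients or visits. The statistical price is the roughly one power point given above if the three factors turn out not to be prognostic.

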2.8.2 Cardiac Symptom distress

The Cardiac Symptom Survey (CSS) was developed by Nieveen et al. (2008) over 20 years ago to assess the symptoms experienced by cardiac surgery patients, particularly those undergoing coronary artery bypass grafting (CABG). The questionnaire includes 10 symptoms, which are evaluated on two dimensions—frequency and severity—ranging from 0 (none) to 10 (extremely severe) (Subih et al., 2018). The specific symptoms listed on the scale include angina, shortness of breath, fatigue, depression, sleep disturbances, incisional pain, leg edema, palpitations/rapid heartbeat, anxiety, and loss of appetite. The frequency and severity scores for each symptom are combined and averaged to reflect the overall level of symptom distress, with higher scores indicating more severe distress. The traditional Chinese version was developed by Yang et al. (2014), with a content validity index of 0.97 and an internal consistency reliability coefficient of 0.95.

2.8.3 Self-care behavior

This scale was developed by Yu et al. (2008) for patients undergoing coronary artery bypass surgery. The scale consists of 16 questions, focuses on patient self-care activities and controlling risk factors (e.g., not smoking, taking medications correctly, regularly measuring blood pressure, attending follow-up appointments, exercising regularly, and controlling diet). The questionnaire uses a 4-point Liker scale, with 4 points for “always” and 1 point “never”,

and total scores ranging from 16 to 64, with higher scores indicating better self-care practices. The scale has a content validity index of over 0.85 and an internal consistency reliability of 0.75.

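### The within-arm before-after test of self-care mixes the move from ward to home with a change in behaviour, so the self-care conclusion should rest on the between-arm difference adjusted for T0

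*Combined protocol and SAP*

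**What the plan says.** - **Timing (section 2.8).** "Outcomes were evaluated at three time points: two days before discharge (baseline, T0"). The later assessments are "at the first outpatient visit (7–10 days post-discharge, T1), and at the end of the intervention (4 weeks post-discharge, T2"). T0 is therefore taken in hospital, and T1 and T2 after the patient has gone home.
- **Recruitment (section 2.1).** "Participants were recruited postoperatively and randomly assigned to either the experimental or control group before hospital discharge". There is no measurement before surgery.
- **Instrument (section 2.8.3, Self-care behavior).** There are 16 items, each scored 1 to 4, with "total scores ranging from 16 to 64, with higher scores indicating better self-care practices". The behaviours listed as examples are "not smoking, taking medications correctly, regularly measuring blood pressure, attending follow-up appointments, exercising regularly, and controlling diet". No recall period, inpatient form or rule for inapplicable items is given. The SF-12 section, by contrast, states a four-week period.
- **Analysis (section 2.9).** A paired t test compares the means "of the scores in each group before and after the interventions". An independent t test compares the two groups, and a GEE is used for changes over time in all three outcomes, self-care included. No group-by-time term and no adjustment for T0 is stated.

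**The concern.** A before-after test asks whether the same quantity has moved. Here the circumstances of the answer change between the two occasions. At T0 the patient is on a surgical ward. At T1 and T2 the patient is at home and responsible for medication, diet, blood pressure readings and appointments. A patient who answers for the present at T0 describes behaviour in hospital; one who answers for the time before admission describes habits before surgery. With no stated recall period, both kinds of answer could enter the same T0 mean. A later rise or fall could then reflect the setting, the behaviour, or both.

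Self-care is in the title and the hypothesis, so a significant within-arm change is likely to be read as evidence about the programme. The particular risk is a paired test that is significant in one arm and not in the other being taken as a treatment effect.

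**Working it through.** **1. The plan's own figure.** Inputs from section 2.5: d = 0.50, alpha 0.05, power 0.80. Section 2.9 gives two-tailed tests and section 2.3 gives 1:1 allocation. The two-sample t test needs 63.8, so 64 per arm, or 128 in total (power 0.801). With 20% attrition, 128 / (1 - 0.20) = 160. Both stated figures reproduce. They correspond to a between-arm comparison of means, not to a before-after test.

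**2. Within-arm paired test when only the setting changes.** Suppose behaviour does not change but the score shifts by s standard deviations because of the setting. With equal variances and T0-to-follow-up correlation r, the standardised paired effect is s / sqrt(2(1 - r)), and the noncentrality is that value times sqrt(64) = 8. Both s and r are assumptions, as the documents give neither. Example: s = 0.3 and r = 0.5 give 0.3 / 1 = 0.3 and a noncentrality of 2.4, so the test rejects in 66% of trials.

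| Shift s (SD) | r = 0.2 | r = 0.5 | r = 0.7 |
|---|---|---|---|
| 0.1 | 10% | 12% | 17% |
| 0.2 | 24% | 35% | 53% |
| 0.3 | 46% | 66% | 86% |
| 0.5 | 88% | 98% | 100% |

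The nominal rate is 5%. The table is symmetric in the sign of s, so it holds equally for a fall.

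**3. Between-arm comparison under the same shift.** In 10,000 simulated trials with s = 0.3 in both arms, r = 0.5, 64 per arm and no treatment effect, the between-arm test of change rejected in 4.9%. The shift cancels. In the same simulation exactly one of the two paired tests was significant in 44% of trials, which is how a false contrast between arms could arise from reading the paired tests side by side.

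**4. Precision, by how T0 is used.** With d = 0.50 in units of the follow-up SD and 64 per arm:
- follow-up score alone: effect 0.50;
- unadjusted change score: effect 0.50 / sqrt(2(1 - r));
- T0 as a covariate: effect 0.50 / sqrt(1 - r²), ignoring the one degree of freedom spent.

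Example at r = 0.2: change score 0.50 / 1.265 = 0.395, power 0.60; covariate 0.50 / 0.980 = 0.510, power 0.82.

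| Assumed r | Follow-up only | Change score | T0 as covariate |
|---|---|---|---|
| 0 | 0.80 | 0.51 | 0.80 |
| 0.2 | 0.80 | 0.60 | 0.82 |
| 0.3 | 0.80 | 0.66 | 0.84 |
| 0.5 | 0.80 | 0.80 | 0.90 |
| 0.7 | 0.80 | 0.95 | 0.98 |

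Using T0 as a covariate is at least as good as either alternative at every r shown. The change score falls below the follow-up score alone whenever r is under 0.5.

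**The case against.** The strongest reply is that the trial's question is between arms and section 2.9 already plans an independent t test between groups. The change of setting is common to both arms, so randomisation deals with it. A within-arm test cannot show a telehealth effect for any outcome, whatever the setting of T0. This stands, and it confines the point to the within-arm analyses and to the choice of the main contrast. It does not remove the point, because the plan lists the paired test alongside the others and does not say which analysis carries the self-care conclusion.

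Four stronger readings are tempting, and the documents do not support them:

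- *Staff determine the T0 score.* A reader might infer that ward staff run medication, diet, smoking and blood pressure measurement. No section says so. The item wording and instructions are not reproduced, and a form that asks about the time before admission would make ward routine irrelevant. Placing T0 at about postoperative day 5 would rest on the introduction's background figure, "the average discharge time being day 7 post-surgery", not on this trial's data.
- *The follow-up item cannot apply at T0.* The section names follow-up appointments in general, and a patient with coronary disease may have attended some before a first bypass operation.
- *A known share of the scale is affected.* The six behaviours are examples, and the number of items for each is not given, so no percentage of the 48-point range can be derived.
- *The self-care comparison has power of only 0.60.* That requires an unadjusted change score, which section 2.9 does not name, and r = 0.2, which is an assumption. At r = 0.5 nothing is lost against the stated 0.80, and at r = 0.7 the change score gains. Nor does section 2.5 tie d = 0.50 to self-care.

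**Conclusion.** The point holds for within-arm change. Self-care is scored in hospital at T0 and after discharge at T1 and T2, with no stated recall period, and the plan tests that change in each arm. Neither the paired test nor a GEE time effect without a group term can support a conclusion about self-care.

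The between-arm comparison at T1 or T2 is not biased, and the sample size of 128 (160 with attrition) is not called into question. The size and direction of any shift are unknown; the rejection rates above show only what an assumed shift would do. The power cost is conditional too. It arises only if change from T0 is compared between arms without adjustment and r is below 0.5, and runs from 0.51 at r = 0 to no loss at r = 0.5. A group-by-time GEE that treats T0 as one of the outcomes could behave much like such a change score, which is a reason to specify the model.

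**What to change.** In section 2.9:

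- State that the self-care conclusion rests on the between-arm difference at T2, with T1 as supporting evidence. Estimate it by ANCOVA at each visit, or by a GEE with T1 and T2 as outcomes and terms for treatment group, visit, group by visit, and the T0 score as a covariate.
- Report the within-arm paired tests for self-care as descriptive only.

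In section 2.8.3 (Self-care behavior), state which period patients answered for at T0. If the form did not fix one, say so and report it as a limitation. Keep all 16 items and the 16 to 64 total: dropping items or marking some inapplicable at T0 would break the total and depart from the form whose validity and reliability the section cites.

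The cost is a wording change. T0 is already part of data collection, so no visit, patient or item is added, and the analysis change still applies if recruitment has closed. The downside is that no inferential claim about within-arm change in self-care can be made.
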